### 5.3 Trial Treatments

The treatment to be used in this trial is outlined below in Table 2.

**Table 2. Trial Treatment**

Drug	Dose/ Potency	Dose Frequency	Route of Administration	Regimen/ Treatment Period	Use
Pembrolizumab	200 mg	Q3W	IV infusion	Day 1 of each 3 week cycle	Experimental
Poly-ICLC	1.8mg/mL *	Twice weekly	Intramuscular injection	Day 0/1, 4, 8, 11, 15, 18 of each cycle	Experimental

\*Per manufacturer, drug product is now formulated at the original 1.8/mg/mL “dry” weight which is equivalent to 2.0mg/mL “wet” concentration of Poly-ICLC. This is a label correction for residual water of hydration in the lyophilized components and represents no change in the product or formulation, but simply a calculation correction.

The treatment to be used in this trial will follow the same regimen in both phases; all subjects will receive both poly-ICLC and pembrolizumab on Day 1 of each cycle. The Day 1 dose of poly-ICLC should be administered in the clinic for all cycles, in both phases. This will allow for assessment of AEs/SAEs and application of dose modifications, if needed, prior to dispensing drug for that cycle.

Trial treatment will be given for 17 cycles. If therapy is not interrupted this will be one year of therapy but therapy may extend for more than one year if interruptions are needed. A subject who, after completing 17 cycles of study treatment and, at that time, has a radiologic disease status of SD, PR or CR, may continue to receive study treatment without interruption for an additional year (up to a total of 35 cycles) of study treatment (Second Course Phase/Retreatment Period, section 7.2.13). See section 5.4.2, *Dose Administration*, for details regarding drug administration.

### 5.4 Dose Selection

The rationale for selection of doses to be used in this trial is provided in *Section 4.0, Background and Rationale*.

#### 5.4.1 Dose Modification (Escalation/Titration/Other)

Adverse events (both non-serious and serious) associated with pembrolizumab exposure may represent an immunologic etiology. These adverse events may occur shortly after the first dose or several months after the last dose of treatment. Pembrolizumab must be withheld for drug-related toxicities and severe or life-threatening AEs as per *Table 3* below. See *Section 5.8.1* for supportive care guidelines, including use of corticosteroids.

**Table 3. Dose Modification Guidelines for Drug-Related Adverse Events**

Toxicity	Hold Treatment For Grade	Timing for Restarting Treatment	Treatment Discontinuation
Diarrhea/Colitis	2-3	Toxicity resolves to Grade 0-1	Toxicity does not resolve within 12 weeks of last dose or inability to reduce corticosteroid to 10 mg or less of prednisone or equivalent per day within 12 weeks
	4	Permanently discontinue	Permanently discontinue
AST, ALT, or Increased Bilirubin	2	Toxicity resolves to Grade 0-1	Toxicity does not resolve within 12 weeks of last dose
	3-4	Permanently discontinue (see exception below) a	Permanently discontinue
Type 1 diabetes mellitus (if new onset) or Hyperglycemia	T1DM or 3-4	Hold pembrolizumab for new onset Type 1 diabetes mellitus or Grade 3-4 hyperglycemia associated with evidence of beta cell failure	Resume pembrolizumab when patients are clinically and metabolically stable
Hypophysitis	2-4	Toxicity resolves to Grade 0-1. Therapy with pembrolizumab can be continued while endocrine replacement therapy is instituted	Toxicity does not resolve within 12 weeks of last dose or inability to reduce corticosteroid to 10 mg or less of prednisone or equivalent per day within 12 weeks
Hyperthyroidism	3	Toxicity resolves to Grade 0-1	Toxicity does not resolve within 12 weeks of last dose or inability to reduce corticosteroid to 10 mg or less of prednisone or equivalent per day within 12 weeks
	4	Permanently discontinue	Permanently discontinue
Hypothyroidism		Therapy with pembrolizumab can be continued while thyroid replacement therapy is instituted	Therapy with pembrolizumab can be continued while thyroid replacement therapy is instituted
Infusion Reaction	2 b	Toxicity resolves to Grade 0-1	Permanently discontinue if toxicity develops despite adequate premedication
	3-4	Permanently discontinue	Permanently discontinue
Pneumonitis	2	Toxicity resolves to Grade 0-1	Toxicity does not resolve within 12 weeks of last dose or inability to reduce corticosteroid to 10 mg or less of

			prednisone or equivalent per day within 12 weeks
	3-4	Permanently discontinue	Permanently discontinue
Renal Failure or Nephritis	2	Toxicity resolves to Grade 0-1	Toxicity does not resolve within 12 weeks of last dose or inability to reduce corticosteroid to 10 mg or less of prednisone or equivalent per day within 12 weeks
	3-4	Permanently discontinue	Permanently discontinue
All Other Drug-Related Toxicity c	3 or Severe	Toxicity resolves to Grade 0-1	Toxicity does not resolve within 12 weeks of last dose or inability to reduce corticosteroid to 10 mg or less of prednisone or equivalent per day within 12 weeks
	4	Permanently discontinue	Permanently discontinue

**Note: Permanently discontinue for any severe or Grade 3 drug-related AE that recurs or any life-threatening event.**

a For patients with liver metastasis who begin treatment with Grade 2 AST or ALT, if AST or ALT increases by greater than or equal to 50% relative to baseline and lasts for at least 1 week then patients should be discontinued.

b If symptoms resolve within one hour of stopping drug infusion, the infusion may be restarted at 50% of the original infusion rate (e.g., from 100 mL/hr to 50 mL/hr). Otherwise dosing will be held until symptoms resolve and the subject should be pre-medicated for the next scheduled dose; Refer to Infusion Treatment Guidelines for further management details.

c Patients with intolerable or persistent Grade 2 drug-related AE may hold study medication at physician discretion. Permanently discontinue study drug for persistent Grade 2 adverse reactions for which treatment with study drug has been held, that do not recover to Grade 0-1 within 12 weeks of the last dose.

#### 5.4.1.1 Determining the Recommended Phase 2 Dose (RP2D) of Poly-ICLC:

For the Phase I component of the trial, classical 3+3 design will be employed and will include dose-escalation to determine the RP2D of Poly-ICLC to be combined with pembrolizumab.

- a. We will consider two dose levels, 1 and 2 mg of Poly-ICLC.
- b. A minimum of 3 patients will be treated depending on DLT. Dose level 1 (1mg) will be administered to a cohort of 3 patients.
- c. If 0 out of 3 experience DLT, then dose escalation will proceed to the dose level 2 (2mg).
- d. If one out of three patients experience DLT, a cohort of additional three patients will be assigned to the same dose level (1mg).
- e. If two or more patients of three (or six) patients experience DLT at the first dose level, then enrollment of patients will be stopped.
- f. If a maximum one patient experiences DLT at dose level 2, then the dose will be declared the RP2D.
- g. If 2 or more out of 6 patients experience DLT at the second dose level, then the first dose level (1mg) will be declared the RP2D.

h. The RP2D should have at least 6 patients enrolled at the dose level with a maximum of 1 patient experiencing DLT. Toxicities that occur during the phase II portion of the study will be taken into account in determining the RP2D.

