#### 1) Run In phase

[figure not shown]
- a. Aimed to determine if poly-ICLC can be safely combined with standard dosages of pembrolizumab.
  - i. Poly-ICLC will be administered intramuscularly twice weekly at two dose levels: 1 mg or 2 mg
  - ii. Pembrolizumab will be administered 200 mg IV q3w
- b. Each dose level enrolls 3-6 patients, with the potential for 12 patients if dose limiting toxicity (DLT) occurs at each dosing level.
- c. Patients with any solid tumor that is unresponsive to at least one line of therapy are eligible for the dose escalation phase unless curative options exist

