### 8.5 Analysis of Endpoints

#### 8.5.1 Analysis of Primary Endpoints

- a. A minimum of 3 patients will be treated depending on DLT. Dose level 1 (1mg) will be administered to a cohort of 3 patients. If 0 out of 3 experience DLT, then dose escalation will proceed to the dose level 2 (2mg). If one out of three patients experience DLT, a cohort of additional three patients will be assigned to the same dose level (1mg). If two or more patients of three (or six) patients experience DLT at the first dose level, the trial, then enrollment of patients will be stopped. If a maximum one patient experience DLT at dose level 2, then the dose will be declared the RP2D. If 2 or more out of 6 patients experience DLT at the second dose level, then the first dose level (1mg) will be declared the RD2D. The RP2D should have at least 6 patients enrolled at the dose level with a maximum of 1 patient experiencing DLT.
- b. To assess preliminary evidence of antitumor activity, in terms of Objective Response Rate (ORR). ORR will be calculated as the number of participants with complete response (CR) or partial response (PR) by RECIST criteria, divided by the total number of participant in the dataset. The ORR will be estimated for every estimated and the associated exact 95% CI will be provided.

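### After 0/3 DLTs at 1 mg and failure at 2 mg, rule (g) declares 1 mg the RP2D on three patients, although rule (h) requires six

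*Combined protocol and SAP*

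**What the plan says.** Section 5.4.1.1 labels the design a classical 3+3 with two poly-ICLC levels and writes the steps out:

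- (b), (c): three patients start at 1 mg. With 0 of 3 DLTs, the trial moves to 2 mg.
- (d): with 1 of 3, three more patients are treated at 1 mg.
- (e): "If two or more patients of three (or six) patients experience DLT at the first dose level", enrolment stops.
- (f): with at most one DLT at 2 mg, 2 mg is the RP2D.
- (g): if 2 or more of 6 "experience DLT at the second dose level, then the first dose level (1mg) will be declared the RP2D".
- The last rule, (h), sets a minimum size for whichever dose is chosen: "The RP2D should have at least 6 patients enrolled at the dose level with a maximum of 1 patient experiencing DLT". It then adds a sentence about later data: "Toxicities that occur during the phase II portion of the study will be taken into account in determining the RP2D".

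Section 8.5.1(a) repeats the rule for 2 mg ("If 2 or more out of 6 patients experience DLT at the second dose level", 1 mg is declared) and the six-patient requirement ("The RP2D should have at least 6 patients enrolled at the dose level", with at most one DLT). It omits the sentence on Phase II toxicities.

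Section 8.1 bases the RP2D on an estimated MTD limited to 1/6 (the text has RLT, apparently for DLT). Section 2.1 gives 3 to 6 patients per level, "with the potential for 12 patients if dose limiting toxicity (DLT) occurs at each dosing level". Section 8.4 gives 3 to 12 patients for the escalation. Section 5.10 replaces early withdrawals so that at least three patients are evaluated per level.

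**The concern.** When the first three patients at 1 mg have no DLT, (c) leaves that level at three. If 2 mg then fails, (g) declares 1 mg at once, without any condition on how many were treated there. Rule (h) does not allow an RP2D with three patients. Both rules cannot be followed on this path, and 8.5.1(a) carries the same conflict, so neither section resolves it.

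The RP2D answers the Phase I primary objective and is the dose for up to 27 Phase II patients. On this path the written rule rests it on half the patients that the plan asks for. Without a written step, the choice between (g) and (h) would be made after the DLTs at both levels are known.

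**Working it through.** **The plan's own figure.** The shortest path is two or more DLTs in the first three at 1 mg, then stop: 3 patients. The longest is 6 + 6 = 12. This assumes 3-then-3 cohorts at 2 mg and escalation after 1/6 at 1 mg, which the text does not spell out. The range of 3 to 12 in 8.4 reproduces.

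**Patients at 1 mg when 1 mg is declared.** There are two routes:

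1. 0/3 at 1 mg, then 2 mg fails: three patients at 1 mg.
2. 1/3 and then 0/3 at 1 mg, then 2 mg fails: six patients at 1 mg with one DLT, which satisfies (h).

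Only (d) adds patients at 1 mg, and it does not apply on route 1. With true DLT rate p1 at 1 mg, route 1's share of all declarations of 1 mg is 1 / [1 + 3·p1·(1−p1)²]. That is 0.88 at p1 = 5%, 0.80 at 10%, 0.72 at 20% and 0.69 at 30%.

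**How often route 1 occurs.** The documents give no DLT rates for the combination, so the rates below are assumptions.

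- P(route 1) = (1−p1)³ × P(2 mg fails).
- With six treated at 2 mg, as (h) requires: P(2 mg fails) = 1 − P(at most 1 of 6 at p2).
- If 2 mg were accepted on 0/3: P(2 mg fails) = 1 − [(1−p2)³ + 3·p2·(1−p2)²·(1−p2)³].
- Example at (10%, 30%): 0.729 × (1 − 0.420) = 0.423.

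**How often completing six would change the answer.** After 0/3, 1 mg fails (h) only if at least two of the three added patients have a DLT: 3·p1²·(1−p1) + p1³. That is 0.007, 0.028, 0.104 and 0.216 at p1 = 5%, 10%, 20% and 30%. Multiplying by P(route 1) gives the share of all trials in which 1 mg would be overturned.

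| Assumed DLT rates (1 mg, 2 mg) | P(route 1), six at 2 mg | P(route 1), 2 mg accepted on 0/3 | Trials in which six at 1 mg overturns it (six at 2 mg) |
|---|---|---|---|
| 5%, 10% | 0.098 | 0.080 | 0.0007 |
| 5%, 20% | 0.295 | 0.250 | 0.0021 |
| 10%, 30% | 0.423 | 0.369 | 0.0118 |
| 10%, 33% | 0.468 | 0.412 | 0.0131 |
| 20%, 40% | 0.393 | 0.354 | 0.0408 |
| 30%, 50% | 0.305 | 0.284 | 0.0660 |

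**What three patients show.** The exact one-sided 95% upper limit for the DLT rate is 1 − 0.05^(1/3) = 63% after 0/3. It is 1 − 0.05^(1/6) = 39% after 0/6, and 58% after 1/6.

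**Size with the missing step added.** Route 1 becomes 3 + 3 + 3 = 9 or 3 + 6 + 3 = 12, so the stated maximum holds.

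**The case against.** The strongest reply is that (h) already answers the question. Rule (f) has the same form as (g): it declares a dose without giving a denominator, and no rule expands 2 mg to six. A reader who lets (h) qualify (f) should let it qualify (g), and then 1 mg must reach six before it is declared. The 12-patient ceiling leaves room for that. This stands as evidence of intent, but it does not supply the step. Rule (g) at least names six patients at 2 mg, whereas nothing sends enrolment back to 1 mg. Section 2.1 links 12 patients to a DLT at each level, and on this path 1 mg has had none. The 3+3 label does not settle it either, because three per level lies within the stated 3 to 6.

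A second reply is that (h) lets Phase II toxicities count, so the six could be completed there. The sentence gives no number, threshold or procedure and is absent from 8.5.1(a). Sections 2.1 and 8.1 describe Phase II as dosed at an RP2D already chosen. A reader might go on to infer that a particular number of Phase II patients would be exposed before the six were complete. The documents do not say that Phase II patients complete the six, so no such figure can be derived.

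A reader might also infer that, if two or more of six at 1 mg had a DLT, nothing decides between stopping under (e) and declaring 1 mg under (g). That is not supported. Rule (e) covers three or six patients at the first level and is not limited to the time before escalation. Rule (h) and the 1/6 limit in 8.1 also exclude 1 mg in that case.

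Finally, the point may be moot for conduct. The protocol history runs to Amendment 10 in November 2022. Inclusion criterion 4 speaks of reconsenting Phase I patients, and footnote 12 of the flow chart extends tissue collection to them from Amendment 4. This suggests, but does not prove, that Phase I enrolment is over.

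**Conclusion.** The contradiction is real but modest. After 0/3 at 1 mg and failure at 2 mg, (g) and its copy in 8.5.1(a) declare an RP2D that (h) does not allow, and no step adds the missing three patients. The intent can be read from (h), (e) and 8.1.

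The path is not remote: probability about 0.10–0.47 under the assumed rates with six treated at 2 mg, and 69–88% of all declarations of 1 mg for 1 mg rates from 30% down to 5%. These are chances of reaching the gap. A reader might take them as chances of choosing a wrong dose, which they are not: completing six would overturn 1 mg in about 0.1–7% of trials, and in about 1% or less when the 1 mg rate is 5–10%. All of these figures rest on assumed DLT rates and binomial cohorts. The conflict between the two rules rests on the text alone.

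**What to change.** In 5.4.1.1(g), and in 8.5.1(a) with the cross-reference adapted, write:

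> If two or more patients at 2 mg have a DLT, stop enrolment at 2 mg; if only three patients have been treated at 1 mg, enrol three more at 1 mg, and declare 1 mg the RP2D only if at most 1 of 6 has a DLT; otherwise stop as in (e).

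The cost is one sentence in each section and up to three more patients at 1 mg, only if 2 mg fails. At the expected 3 patients per month this is about one month of accrual (3 ÷ 3) plus the 3-week DLT window.

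If Phase I is already complete, no enrolment change is needed. Report the patients treated and the DLTs at each level, and state which rule was applied, so that readers can see whether the RP2D met (h).

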**5.4.1.2 Dose Limiting Toxicity (DLT) Criteria for poly-ICLC escalation phase:**

A DLT will be defined as any Grade  $\geq 3$  or higher treatment-related toxicity that occurs during the DLT-evaluation period. Toxicity that is clearly and directly related to the primary disease or to another etiology is excluded from this definition. The following will be DLTs, regardless of relatedness:

- Any Grade 4 irAE
- Any Grade 4 non-hematologic toxicity
- Any Grade  $\geq 3$  diarrhea or vomiting that does not resolve within 3 days
- Any Grade 3 irAE, excluding colitis or pneumonitis, which does not downgrade to  $\leq$  Grade 2 within 3 days after onset of the event despite maximal medical supportive care including systemic corticosteroids or does not downgrade to  $\leq$  Grade 1 or baseline within 14 days.
- Any  $\geq$  Grade 3 colitis irrespective of duration
- Any Grade  $\geq 3$  non-infectious pneumonitis irrespective of duration
- Liver transaminase elevation  $\geq 5 \times$  but  $\leq 8 \times$  ULN that does not downgrade to Grade 2 within 5 days after onset with optimal medical management, including systemic corticosteroids. Transaminase elevation  $> 8 \times$  ULN or total bilirubin  $> 5 \times$  ULN will be considered a DLT regardless of duration or reversibility
- Any increase in AST or ALT  $> 3 \times$  ULN and concurrent increase in total bilirubin  $> 2 \times$  ULN (Hy's Law).

The definition of DLT *excludes* the following conditions:

- Grade 3 fatigue for  $\leq 7$  days
- Grade 3 endocrine disorder (thyroid, pituitary, and/or adrenal insufficiency) that is managed with or without systemic corticosteroid therapy and/or hormone replacement therapy
- Grade 3 inflammatory reaction attributed to a local antitumor response that resolved to  $\leq$  Grade 1 within 30 days
- Concurrent vitiligo or alopecia of any AE grade
- Grade 3 infusion-related reaction (IRR; first occurrence and in the absence of steroid prophylaxis) that resolves within 6 hours with appropriate clinical management.
- Grade 3 neutropenia that is not associated with fever or systemic infection that improves by at least 1 grade within 3 days.
- Grade 3 or Grade 4 lymphopenia (unless clinically significant)
- Grade 3 thrombocytopenia that is not associated with clinically significant bleeding that requires medical intervention, and improves by at least 1 grade within 7 days
- Isolated Grade 3 electrolyte abnormalities that are not associated with clinical signs or symptoms and are reversed with appropriate maximal medical intervention within 3 days
- Grade 3 fever lasting  $\leq 24$  hours with or without medical therapy and is not considered a serious adverse event

**The period for definition of DLT will be the first 3 weeks of treatment.** Dosing interruptions are permitted in the case of medical / surgical events or logistical reasons not related to study therapy (e.g., elective surgery, unrelated medical events, patient vacation, and/or holidays). Subjects should be placed back on study therapy within 3 weeks of the scheduled interruption, unless otherwise discussed with the Sponsor. The reason for interruption should be documented in the patient's study record.

#### **5.4.2 Dose Administration**

Trial treatment should be administered on Day 1 of each cycle after all procedures/assessments have been completed as detailed on the Trial Flow Chart (Section 6.0). Trial treatment may be administered up to 3 days before or after the scheduled Day 1 of each cycle due to administrative reasons.

##### **5.4.2.1 Pembrolizumab Preparation, Storage and Administration**

Pembrolizumab 200 mg will be administered as a 30 minute IV infusion on an outpatient basis every 3 weeks. Sites should make every effort to target infusion timing to be as close to 30 minutes as possible. However, given the variability of infusion pumps from site to site, a window of -5 minutes and +10 minutes is permitted (i.e., infusion time is 30 minutes: -5 min/+10 min). Preparation and administration of the investigational agent, pembrolizumab, will follow the same guidelines as for the FDA-approved agent, pembrolizumab, known commercially as Keytruda.

###### Preparation for Intravenous Infusion

- Visually inspect the solution for particulate matter and discoloration prior to administration. The solution is clear to slightly opalescent, colorless to slightly yellow. Discard the vial if visible particles are observed.
- Dilute pembrolizumab injection (solution) or reconstituted lyophilized powder prior to intravenous administration.
- Withdraw the required volume from the vial(s) of pembrolizumab and transfer into an intravenous (IV) bag containing 0.9% Sodium Chloride Injection, USP or 5% Dextrose Injection, USP. Mix diluted solution by gentle inversion. The final concentration of the diluted solution should be between 1 mg/mL to 10 mg/mL.
- Discard any unused portion left in the vial.

###### Storage of Diluted Solutions

The product does not contain a preservative. Store the diluted solution of pembrolizumab either:

- At room temperature for no more than 6 hours from the time of dilution. This includes room temperature storage of the infusion solution in the IV bag, and the duration of infusion.
- Under refrigeration at 2°C to 8°C (36°F to 46°F) for no more than 24 hours from the time of dilution. If refrigerated, allow the diluted solution to come to room temperature prior to administration. Do not freeze.

###### Administration

- Administer infusion solution intravenously over 30 minutes through an intravenous line containing a sterile, non-pyrogenic, low-protein binding 0.2 micron to 5 micron in-line or add-on filter.
- Do not co-administer other drugs through the same infusion line.

- The first injection of Pembrolizumab will be administered in clinic one hour after the first IM injection of Poly ICLC in the concurrent treatment group under the supervision of study clinical staff. Pembrolizumab will be administered one day after Poly ICLC injection in the subsequent treatment group. These two groups apply to phase II, while phase I will follow similar schedule as concurrent treatment group.
- The patient will be monitored for at least 30 minutes including a determination of blood pressure, heart rate, and respiratory rate before and after each injection.

#### **5.4.2.2 Poly-ICLC Preparation, Storage and Administration**

Poly-ICLC is provided in vials containing 1.8mg (1 ml). Excess volume is expected for the first cohort of subjects (1 mg/ .5ml). Unless labeled otherwise, the poly-ICLC vials being provided for this trial are labeled as single-use; therefore excess volume will be discarded. For doses that are administered at the clinical site, staff will dispose of the vials according to local protocol. For doses that are administered at the subject's home, used vials should be kept and returned to clinical staff at the following visit for reconciliation/compliance assessment.

Study subjects will receive intramuscular (IM) injections of 1 or 2 mg poly-ICLC on Days 1, 4, 8, 11, 15, 18 of each three-week cycle (twice weekly). The first injection of each cycle will be administered in clinic under the supervision of study clinical staff. The subject will be monitored for at least 30 minutes after the first IM injection; blood pressure, heart rate, and respiratory rate should be assessed before and after injection. Approximately one hour after the poly-ICLC injection is given, the subject will begin pembrolizumab IV infusion.

Following the first treatment, subsequent poly-ICLC injections may be administered at home by the study subject or the study subjects' person of choice (e.g., family member, friend). Study subjects will be given a set of written instructions to follow, and a diary sheet that they are required to maintain showing the dates and times when injections were given and the injection sites (extremities). At the investigator's discretion, subsequent injections may be scheduled to be given in the outpatient clinic instead of at-home administration.

IM injections will be performed using standard technique into the thighs or upper arms. Injection site may be rotated based on study subjects' and investigator preference and will be recorded in the diary. The study nurse will train the study subjects or the study subjects', person of choice on how to inject IM Poly-ICLC during the first treatment.

The investigational pharmacy will follow its standard operating procedures (SOPs) when dispensing the study drug for distribution to the study subjects. Study subjects will be instructed to administer (or have their person of choice administer) the second IM injection 3 days following the first injection (Day 4). The clinical staff will provide study subjects with a sufficient supply of Poly-ICLC, sterile syringes with needles and alcohol swabs for this purpose. Study subjects will be instructed to store the vials in the refrigerator, in a location that prevents the study drug from freezing, until it is time to administer the study drug. They will be told to exchange any vials of Poly-ICLC that inadvertently becomes frozen.

The study subjects will also be provided with a diary wherein the date, time and injection site of the study drug is to be noted as well as comments on any side effects. The diary will be reviewed by the clinic staff with the study subject at clinic visits and collected from the study subject at the following

study visit. Study subjects and/or their person of choice will be instructed to allow a 72-hour interval between each injection. Study subjects will be instructed to contact the study doctor with any concerns regarding injections.

